### **10.4. Electrocardiography (ECG)**

ECG parameters (PR, QRS, RR, and QT) will be summarized by baseline and change from baseline to each scheduled and collected assessment time.

ECG status (i.e. normal, abnormal) will be reported. Shift tables will be provided to present the post-baseline status according to the baseline status (normal or missing / abnormal) for each cohort.

### **10.5. Other Safety Data**

Other safety data, such as data collected from physical examination that includes head and neck, lungs, heart, abdomen, lymph nodes, extremities, skin, a brief neurologic examination, and ECOG performance status, etc, will be analyzed when necessary.

## 11. DATA CONVENTIONS

The following analysis conventions will be used in the statistical analysis.

### 11.1. Definition of Baseline for Efficacy/Safety Variables

Unless otherwise specified, the baseline assessment for all measurements will be the latest available valid measurement taken prior to the administration of investigational product.

### 11.2. Data Convention

For categorical variables, patients with missing data are not included in calculations of percentages unless otherwise specified. When relevant, the number of patients with missing data is presented.

Patients who are deemed unevaluable (NE) per RECIST 1.1 will be considered as not reaching CR/PR/SD in calculating ORR/DCR, i.e. they are not considered as responders in the numerator of ORR/DCR, but they are counted in the denominator of ORR/DCR.

Last contact date will be derived from all assessments (e.g., tumor assessments) and actual event dates (e.g., AEs, biopsy, etc).

#### Incomplete Death dates

If death year is completely missing, it will be imputed as the last known alive date +1. If month and day are missing, death date will be imputed to max (1 Jan of the year of death, last known alive date +1). If only day is missing, death date will be imputed to max (1st day of month and year of death, last known alive date +1).

### 11.3. Data for Non-Efficacy Endpoints

#### Incomplete Medication dates

If medication start date is completely missing, impute it to min (first dose date of any study drug, medication end date). If medication start month is missing, and medication start year is not missing: If medication start year is less than the first dose year, use the first day of the year. If medication start year is equal to the first dose year, use the first dose day and month. Else impute the day and month using 01 January. If this leads to a date after the medication end date, use medication end date instead. If medication start day is missing, and medication start month and year are not missing: If medication start year is the same as first dose year and the medication start month is the same as the first dose month, then impute medication start day using the day of first dose. If this leads to a date after the medication end date, use medication end date instead. Otherwise impute the medication start day using the first day of the month.

If medication end date is completely missing, do not impute. It's an ongoing medication. If medication end month is missing, and medication end year is not missing: Impute end date to the earlier of (reference end date, 31DECYYYY). If concomitant medication end day is missing, and concomitant medication end month and year are not missing: Impute end date using the last day of the month.

If post treatment anti-cancer therapy start month or year is missing, do not impute the date. If post-treatment anticancer therapy start day is missing, and start month and year are not missing: impute

the start day using the 15th day of the month. If this leads to a date on or before the last dose (of original treatment) date, use last dose date+1 instead.

#### **Adverse event**

If the NCI grade of a TEAE is missing, it will not be imputed. A TEAE with missing grade will be summarized under all grades in the TEAE frequency tables. If the assessment of relationship of a TEAE to the investigational product is missing, it will be classified as related to the investigational product.

#### **Date of first / last study treatment**

Date of first infusion is the first non-missing start date of dosing filled in the CRF “Investigational Product” module.

If a patient’s date of the last dose is totally missing or unknown, his/her last visit date will be substituted.

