Abbreviations: 100DFU = 100-Day Follow-up; ACTH = adrenocorticotrophic hormone; AE = adverse event; BMI = body mass index; CNS = central nervous system; d = day; CR = complete response; CRS = cytokine release syndrome; CT = computed tomography; ECG = electrocardiogram; ECOG = Eastern Cooperative Oncology Group; EOT = end of treatment; FSH = follicle-stimulating hormone; INR = international normalized ratio; IT = intratumorally; LTSFU = long-term survival follow-up; MRI = magnetic resonance imaging; n/a = not applicable; PD = progressive disease; PD-1 = programmed cell death protein 1; PD-L1 = programmed death-ligand 1; PE = physical examination; PR = partial response; PT = prothrombin time; PTFU = posttreatment follow-up; PTT = partial thromboplastin time; Q3W = every 3 weeks; Q3mo = every 3 months; Qb = Qbeta; QTc = QT corrected; RECIST = Response Evaluation Criteria in Solid Tumors; SC = subcutaneously; W = week; WOCBP = women of childbearing potential.

a. The W4D2 visit is mandatory but may be waived under certain circumstances. The site must contact the medical monitor for a waiver. (Note: Footnote "a" is not applicable from Protocol Amendment 5)

b. End of Treatment assessments are to be performed within 30 days (±7 days) after subject discontinuation from last study treatment. Subjects who discontinue vidutolimod but continue on treatment with cemiplimab will have separate EOT visits for both vidutolimod and cemiplimab. Removal of a subject from vidutolimod treatment is defined as the time in which the Investigator decides to discontinue study treatment. If a subject has vidutolimod dosing withheld for more than 3 consecutive doses for any reason during the Q3W dosing period, resumption of treatment must be discussed with the Medical Monitor; otherwise, the subject will be discontinued from study treatment and will have all EOT assessments performed.

- c. AEs and concomitant medications data will be collected until 100 days (± 7 days) after the last dose of study drug (vidutolimod or cemiplimab) or until an alternative anticancer treatment is initiated, or until overall End of Clinical Trial (Section 3.4), whichever occurs first. The 100DFU should occur 100 days (± 7 days) from the last study treatment (vidutolimod or cemiplimab) and may be conducted at the study site or via phone.

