- d. Posttreatment follow-up (PTFU) will be conducted Q3mo (± 2 weeks) for all subjects who discontinue study treatment but have not met criteria for study discontinuation. These subjects should remain on study and receive disease assessments Q3mo, until disease progression or discontinuation of PTFU for any reason. For an individual subject, the maximum duration of PTFU is 18 months. After completing PTFU, subjects go to LTSFU.
- e. LTSFU will be conducted Q3mo (± 4 weeks) after the EOT visit or the last disease assessment date in PTFU and may occur via phone. LTSFU may continue until overall End of Clinical Trial (Section 3.4).
- f. Vidutolimod dosing will begin on W1D1. A window of ± 2 days is permitted for vidutolimod weekly dosing from W1D1 to W7D1. The first dose of vidutolimod may be administered SC or IT, at the discretion of the Investigator; all subsequent doses are planned to be administered IT until no injectable lesions remain. Subjects must complete all 7 weekly vidutolimod doses before moving to the Q3W dosing schedule. Q3W dosing (W10D1+): A window of ± 3 days is permitted for vidutolimod dosing from W10D1 throughout the study. When cemiplimab treatment is permanently discontinued, vidutolimod must also be permanently discontinued. Refer to Section 4.3 for treatment compliance.
- g. Treatment with cemiplimab will begin on W1D1 and continue Q3W throughout the study. When vidutolimod injection and cemiplimab dosing fall on the same day, vidutolimod injection will be given before cemiplimab. Refer to Section 4.1.2 for details of cemiplimab dosing.
- h. A full PE will be conducted at Screening and EOT. If the Screening full PE is performed >72 hours before the W1D1 visit, then a brief (symptom directed) PE must be performed within 72 hours before the first injection of vidutolimod. Brief PEs focused on areas of disease or AEs must be performed at every vidutolimod injection visit (before vidutolimod administration), and at any other time as clinically indicated. Height will be obtained at Screening only and weight at all PE assessments.

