#### 1. Duration of Exposure

Duration of exposure will be calculated as follows:

Duration of exposure (weeks) = (first dose date of the last cycle received + corresponding cycle duration – first dose date) / 7

- For CMP-001, the corresponding cycle duration = 7 days for Week 1 through Week 6 of Q1W schedule and 21 days for Week 7 and the following Q3W schedule
- As for Cemiplimab, the corresponding cycle duration is 21 days

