#### 2. Dosing Intensities

(1) Actual dose intensity (mg/week) will be calculated as the total actual cumulative dose received divided by duration of exposure (weeks) for CMP-001 and Cemiplimab, respectively.

(2) Planned dose intensity (mg/week) will be calculated as the total planned cumulative dose to be received divided by the planned exposure duration (weeks) based on the protocol schedule.

Planned Exposure Duration (weeks) = number of planned treatments \* corresponding cycle duration (weeks)

- For CMP-001, the corresponding cycle duration = 1 week for Week 1 through Week 6 of Q1W schedule and 3 weeks for Week 7 and the following Q3W schedule
- As for Cemiplimab, the corresponding cycle duration is 3 weeks

(3) Relative dose intensity (%) will be calculated based on the actual cumulative dose received relative to the planned cumulative dose throughout the exposure duration as follows:

Relative dose intensity (%) = (actual dose intensity / planned dose intensity) \* 100%

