## 10. ANALYSIS OF SAFETY DATA

The analysis of safety and tolerance will be performed on the SAF .

The safety analysis will be based on the reported AEs and other safety information (clinical laboratory evaluations, vital signs and 12-lead ECG, etc.).

For safety variables, 3 observation periods are defined:

- The pre-treatment period is defined as the time from signing the screening ICF to before the first dose of study drug.
- The on-treatment period is defined as the time from first dose of study drug to the last dose of study drug plus 100 days or until the start of new systemic therapy for treatment of the patient's tumor (whichever is earlier).
- The post-treatment period is defined as the time starting 1 day after the end of on-treatment period.

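### SAP 11.3 sets an unknown last-dose date to the last visit date without limiting it to dosing visits, so the imputed date can fall weeks to about 18 months late

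*SAP*

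**What the plan says.** Under its heading on the dates of first and last study treatment, SAP 11.3 takes the first dose from the earliest dosing record in the Investigational Product module. For the last dose it uses a different source: where a patient's "date of the last dose is totally missing or unknown, his/her last visit date will be substituted". The SAP does not define the last visit, does not limit it to visits at which drug was given, and does not say whether the rule applies to each drug separately.

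The last-dose date is used in several places:
- SAP 10 runs the on-treatment period from first dose to "the last dose of study drug plus 100 days or until the start of new systemic therapy", whichever is earlier.
- SAP 9.2 classes a medication as concomitant up to 100 days after the last dose, or until new anticancer treatment if that is earlier.
- SAP 9.1 computes exposure from the "first dose date of the last cycle received + corresponding cycle duration", less the first-dose date, divided by 7. Actual dose intensity is cumulative dose divided by that duration.
- SAP 11.3 imputes a day-missing start of subsequent anticancer therapy as the 15th of the month, and adds: "If this leads to a date on or before the last dose (of original treatment) date, use last dose date+1 instead".

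Protocol Table 1 schedules contacts after dosing has ended. Footnote b: "End of Treatment assessments are to be performed within 30 days (±7 days) after subject discontinuation from last study treatment". Footnote c places a follow-up at 100 ± 7 days after the last dose, by office visit or phone. Footnote d sets PTFU visits every 3 months: "For an individual subject, the maximum duration of PTFU is 18 months". Survival contacts follow.

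**The concern.** For a subject who has stopped treatment, the last visit is by design usually later than the last dose. Protocol 3.4 itself puts the last subject's last visit about 100 days after the last dose. A rule that equates the two dates can then err in one direction only, making the last dose too late. The size of the error depends on how long the subject was followed, which has nothing to do with how long the subject was treated.

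Most directly at stake are the two windows tied to last dose plus 100 days. Exposure duration and dose intensity are also at stake if the imputed date enters the SAP 9.1 formula. The per-drug gap adds to this. Footnote b lets a subject stop vidutolimod and stay on cemiplimab, so a missing vidutolimod date could be replaced by a visit well into cemiplimab treatment.

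**Working it through.** The plan gives no figure to reproduce. The check is date arithmetic on its own schedule.

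**Inputs.** EOT at 30 ± 7 days, 100-day follow-up at 100 ± 7 days and PTFU to 18 months (Protocol Table 1, footnotes b–d). On-treatment tail of 100 days (SAP 10). Final cycle length of 21 days for vidutolimod from Week 7 and for cemiplimab throughout (SAP 9.1). Vidutolimod 10 mg per dose (Protocol 4.1.1). I take one month as 30.44 days, so 18 months is 548 days. I count all visits from the last dose. Footnote b counts EOT from discontinuation and allows it to be earlier, so the EOT range is nominal. Counting PTFU from an EOT visit at day 37 would give 548 + 37 = 585 days, or 19.2 months.

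**Step 1: lateness and window.** Lateness = day of last visit − day of true last dose. Tail = 100 + lateness, unless new systemic therapy ends it sooner.

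| Last visit | Late by (days) | Tail after true last dose (days) |
|---|---|---|
| Visit of the last dose | 0 | 100 |
| EOT | 23–37 | 123–137 |
| 100-day follow-up | 93–107 | 193–207 |
| PTFU at 18 months | about 548 | about 648 |

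**Step 2: exposure and dose intensity.** SAP 9.1 refers to the first dose date of the last cycle, not to the last-dose date. With one dose per cycle these are the same day, so I assume here that the imputed date is used. Exposure in weeks = (day of last dose + lateness + 21)/7, counting W1D1 as day 0.

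Vidutolimod stopped after dose 7 (W7D1, day 42, 70 mg):
- True: (42 + 21)/7 = 9.0 weeks; 70/9.0 = 7.78 mg/week.
- EOT, +30 days: 93/7 = 13.3 weeks; 5.27 mg/week.
- 100-day follow-up: 163/7 = 23.3 weeks; 3.01 mg/week.
- PTFU at 18 months: 611/7 = 87.3 weeks; 0.80 mg/week.

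Planned intensity for these seven doses is 70/(6 × 1 + 3) = 7.78 mg/week. Relative dose intensity therefore falls from 100% to 63/93 = 67.7%, 63/163 = 38.7% and 63/611 = 10.3%.

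The effect is smaller after longer treatment. With a last dose at W28D1 (day 189) and all doses given, exposure is 210/7 = 30.0 weeks. It becomes 34.3, 44.3 and 108.3 weeks, and relative dose intensity becomes 87.5%, 67.7% and 27.7%. The percentages are the same for cemiplimab.

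**Step 3: effect on a cohort.** One affected subject among 25 moves mean exposure by 30/25 = 1.2 days (EOT), 100/25 = 4 days (100-day) or 548/25 = 21.9 days, about 3.1 weeks (18-month PTFU). The maximum can move by the full amount; the median should move little.

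**The case against.** The strongest reply is that the rule will rarely be used. Both drugs are given by site staff (Protocol 4.3), the date and time of every dose are listed (Protocol 8.5), and there is drug accountability and source data verification (Protocol 5.3 and 9.1). The large errors are also the least likely. The 100-day contact is timed from the last dose, so a site that makes it will normally know that date. Subjects who withdraw from the study have no EOT or safety follow-up visit (Protocol 3.3), so their last visit may well be a dosing visit. All of this stands. It limits how often the rule is used, but does not make it right when the last visit falls after treatment.

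A reader might infer that treatment-emergent event counts are materially inflated. The documents do not support that. After 100 days only treatment-related SAEs are recorded (Protocol 6.4.1), and SAP 10.1 already counts these as treatment-emergent. The remaining gap is Protocol 7.3.1, which also lets other related events be recorded after 100 days.

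A reader might also infer that PFS and DOR censoring is wrong for every affected subject. It is not. SAP 7.1 censors at the last valid assessment on or before new therapy. A change therefore needs a missing last-dose date, a therapy start whose day is also missing, and a scan between the true and imputed start dates. PTFU assessments stop once another cancer treatment begins (Protocol 6.6), so such a scan is unlikely.

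Finally, SAP 9.1 does not refer to SAP 11.3, so the exposure effect is an inference. That is correct, and the figures in Step 2 depend on it.

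**Conclusion.** The rule as written is wrong for this design, with modest consequences. When the last visit falls after treatment, the imputed last dose is late by roughly 23–37 days (EOT), 93–107 days (100-day follow-up) or up to about 18 months (PTFU). The on-treatment and concomitant-medication windows lengthen to match. The main distortion would be in exposure and dose intensity, provided the imputed date is used in SAP 9.1.

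It would be too strong to say that exposure and the safety window run long across the trial, or that every use of the rule gives a wrong date. The rule needs a wholly missing or unknown last-dose date, and the lateness is zero if the last visit was the visit of the last dose. The documents give no rate of missing dates; on-site dosing suggests it is low. The 18-month figure is a nominal PTFU limit, not a strict ceiling. It is exceeded if PTFU is counted from EOT, if survival contacts count as visits, or if a vidutolimod date is missing in a subject who continued cemiplimab. A correction is worthwhile because the error is one-sided and costs almost nothing to remove.

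**What to change.** Replace the sentence in SAP 11.3 with wording such as:

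> If the date of last dose is missing for a drug, use the date of the last visit at which a dose of that drug was recorded as given in the Investigational Product module. If that visit date is also unavailable, use the last non-missing dosing date for that drug. The imputed date may not be later than the earliest of the EOT visit, the start of new anticancer therapy and death. Visits after treatment discontinuation are not used. Affected subjects will be listed.

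The order matters. Going straight to the last non-missing dosing date would pick an earlier dose whenever the final dose's own date is the missing one, and so shorten exposure and the safety window. As the second choice only, it carries that downside in few cases. If just the final date is missing, the shortfall is about one dosing interval: 7 days in the weekly phase and 21 days afterwards.

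A cross-reference from SAP 9.1, saying that the same imputed date is used for the last cycle, would remove the inference in Step 2. The cost is a short SAP amendment and one listing, with no new data.

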### **11.4. Assignment of Data to Visit Windows and Unscheduled Assessments**

Assessments taken outside of the allowable windows will be displayed according to the case report form assessment recorded by the investigator. All scheduled assessments will be summarized by the nominal visit number and no visit windows will be defined.

#### **Unscheduled Assessments**

Unscheduled visit measurements may be used for both efficacy and safety variables to provide a measurement for a baseline or endpoint value if appropriate according to their definition

## 13. APPENDIX

### 13.1. Summary of Statistical Analyses

#### Efficacy Analysis – phase 2

Endpoint	Analysis Populations	Statistical Method per Cohort	Supportive Analysis	Subgroup Analysis	Other Analyses
ORR per RECIST1.1	FAS	ORR, along with 95% CI by using Clopper-Pearson method	No	Yes	Maybe
DCR	FAS	DCR, along with 95% CI by using Clopper-Pearson method	No	No	Same as above
TTR	FAS	Median, range	No	No	Same as above
DOR	FAS	KM estimates, range	No	No	Same as above
PFS	FAS	KM estimates	No	No	Same as above
OS	FAS	KM estimates	No	No	Same as above

Signature Page for VV-RIM-00379701 v1.0

Approval/eSignature		
		19-Nov-2024 20:50:20 GMT+0000

Approval/eSignature		
		20-Nov-2024 04:18:54 GMT+0000

Signature Page for VV-RIM-00379701 v1.0 Approved
